#### 5.2.1. Analyses for Binary Data

#### 5.2.1.1. Immunogenicity Data

CCI

The exact CIs for a proportion will be computed using the F distribution. If r is the number of responses and n is the number of participants, then it follows that p = r/n is the estimate of the proportion of responses. An exact 95% CI can be computed by solving the following 2 equations. For the lower limit  $P_L$ , use

$$p_L = \frac{rF_L}{(rF_L + (n-r+1))}$$

and for the upper limit Pu, use

$$p_U = \frac{(r+1)F_U}{(n-r) + (r+1)F_U}$$

where  $F_L$  is the quantile from the F distribution for  $\alpha$ =0.025, with numerator degrees of freedom equal to 2r and denominator degrees of freedom equal to 2(n-r+1).  $F_U$  is the quantile from the F distribution for  $\alpha$ =0.975, with numerator degrees of freedom equal to 2(r+1) and denominator degrees of freedom equal to 2(n-r). When r equals 0,  $F_L$  should be set equal to 1.0 so  $P_L$  equals 0. When r equals n,  $F_U$  should be set equal to 1.0 so  $P_U$  equals 1.

The CI using the F distribution is described by Collett (1991).3

#### 5.2.1.3. Safety Data

Similarly, the exact 2-sided 95% CIs using the Clopper and Pearson method will be provided by vaccine group for all primary safety endpoints, proportions of participants reporting local reactions, systemic events (Stage 1 nonpregnant women with primary vaccination [3 vaccine groups], Stage 1 nonpregnant women with booster vaccination [1 vaccine group], Stage 2 maternal participants [7 vaccine groups], and Stage 3 maternal participants [2 vaccine groups]), AEs, SAEs, and MAEs (Stage 1 nonpregnant women with primary vaccination

[3 vaccine groups], Stage 1 nonpregnant women with booster vaccination [1 vaccine group], Stage 2 maternal participants [7 vaccine groups], and Stage 3 maternal participants [2 vaccine groups] and their infants), obstetric complications, delivery outcomes, and delivery mode (Stages 2 and 3 maternal participants), and AEs of special interest (Stages 2 and 3 infant participants).

For Tier 2 AEs only, 95% CIs for the difference in proportions between each GBS6 vaccine group and placebo (risk difference) based on the Chan and Zhang method will be provided for nonpregnant women with primary vaccination (Stage 1), nonpregnant women with booster vaccination (Stage 1), maternal participants (Stages 2 and 3), and infant participants (Stages 2 and 3).

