5.2. Inclusion Criteria – Stage 1 Booster Vaccination

Participants are eligible to be included in the study only if all of the following criteria apply:

- Evidence of a personally signed and dated informed consent document (ICD) indicating that the participant has been informed of all pertinent aspects for the booster vaccination and subsequent visits.
- Participant must have received investigational product at Visit 1.

Final Protocol Amendment 8, 27 March 2023

- Willing and able to comply with scheduled visits, investigational plan, laboratory tests, and other study procedures, including completion of the e-diary from Day 1 to Day 7 following booster vaccination with GBS6.
- Participant continues to meet all Stage 1 inclusion criteria and none of the Stage 1 exclusion criteria (except exclusion criterion 11).
- Healthy nonpregnant female determined by medical history, physical examination, and clinical judgment of the investigator to be eligible for booster vaccination and received investigational product at Visit 1.
- Expected to be available for the duration of the study and who can be contacted by telephone during study participation.
- Negative urine pregnancy test at Visit 6 (prior to vaccination).

Female participants of nonchildbearing potential must meet at least 1 of the following criteria:

- a. Achieved postmenopausal status, defined as follows: cessation of regular menses for at least 12 consecutive months with no alternative pathological or physiological cause; status may be confirmed with a serum follicle-stimulating hormone (FSH) level confirming the postmenopausal state;
- b. Have undergone a documented hysterectomy and/or bilateral oophorectomy;
- Have medically confirmed ovarian failure.

All other female participants (including female participants with tubal ligations) are considered to be of childbearing potential.

 Documented negative HIV, hepatitis C virus (HCV), and acute or chronic hepatitis B virus (HBV) infection at screening.

5.3. Exclusion Criteria – Stage 1

Participants are excluded from the study if any of the following criteria apply:

- Investigator site staff members directly involved in the conduct of the study and their family members, site staff members otherwise supervised by the investigator, or participants who are Pfizer employees, including their family members, directly involved in the conduct of the study.

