6.4. Administration

Standard vaccination practices must be observed, and vaccine must not be injected into blood vessels. Appropriate medication and other supportive measures for management of an acute hypersensitivity reaction should be available in accordance with local guidelines for standard immunization practices.

Preparation and administration of investigational products should be performed by an appropriately qualified, trained, and vaccine-experienced member of the study staff (eg, physician, nurse, physician's assistant, nurse practitioner, pharmacist, or medical assistant) as allowed by local, state, and institutional guidance.

Investigational product administration details will be recorded on the case report form (CRF).

In Stage 1, participants will receive 1 dose of either GBS6, formulated with or without AlPO₄, or placebo (saline control) at Visit 1 in accordance with the study's schedule of activities. All returning participants in Stage 1 will also receive 1 dose of GBS6 (20 µg CPS/serotype/dose with AlPO₄) at Visit 6 in accordance with the study's schedule of activities. Stage 2 participants will receive 1 of 3 possible dose levels of GBS6, formulated with or without AlPO₄, or placebo (saline control) at Visit 1 in accordance with the study's schedule of activities.

In Stage 3, participants will receive 1 selected dose/formulation of either GBS6 or placebo (saline control) at Visit 1 in accordance with the study's schedule of activities.

GBS6 or placebo (saline control) should be administered intramuscularly by preferably of the nondominant arm.

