#### 4.1.1. Per-Protocol Analysis Set: Nonpregnant Women (Stage 1)

The primary vaccination evaluable immunogenicity population will include participants who:

- Are eligible (have signed informed consent and met all inclusion/exclusion criteria) and randomized into the study;
- Have received GBS6 or placebo as randomized;
- Have blood drawn for assay testing within 27 to 49 days, inclusive, after primary vaccine administration at Visit 3 (1 month after vaccination);
- Have at least 1 valid and determinate assay result for the 1-month post-primary vaccination visit;
- Have no major protocol violation as determined by the sponsor's global medical monitor.

The booster vaccination evaluable immunogenicity population will include participants who:

- Are eligible (have signed informed consent and met all inclusion/exclusion criteria) and assigned to the booster vaccination;
- Have received a booster dose of GBS6;

- Have blood drawn for assay testing within 27 to 49 days, inclusive, after booster vaccine administration at Visit 7 (1 month after booster vaccination);
- Have at least 1 valid and determinate assay result for the 1-month after the booster vaccination visit;
- Have no major protocol violation as determined by the sponsor's global medical monitor.

Major protocol violations will be determined by clinical review. A major protocol violation is a protocol violation that, in the opinion of the sponsor's global medical monitor, would materially affect assessment of immunogenicity, eg, participant receipt of a prohibited vaccine or medication that might affect immune response or a medication error with suspected decrease in potency of the vaccine. The sponsor's global medical monitor will identify those participants with protocol violations before any immunogenicity analysis is carried out.

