### 4.2.1. Full Analysis Set: Nonpregnant Women (Stage 1)

The primary vaccination mITT population will include all randomized participants who have at least 1 valid and determinate assay result.

The booster vaccination mITT population will include all randomized participants who received a booster dose and have at least 1 valid and determinate assay result.

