# 4.3.1. Safety Analysis Set: Nonpregnant Women (Stage 1)

All participants who received a primary dose of GBS6 vaccine or placebo will be included in the primary vaccination safety population.

All participants who received a booster dose of GBS6 will be included in the booster vaccination safety population.

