#### 5.2. General Methods

Descriptive summary statistics will be provided for all endpoints. Unless otherwise explicitly stated, the descriptive statistics for continuous variables are: n, mean, median, standard deviation, minimum, and maximum. The descriptive statistics for categorical variables are: the proportion (%), n (the numerator), and N (the denominator) used in the proportion calculation.

The dose/formulation level and vaccine group (hereafter referred to as vaccine group) in this study are defined as below:

- GBS6 (5 μg)/AlPO4
- GBS6 (5 μg)/no AlPO4
- GBS6 (10 μg)/AlPO4
- GBS6 (10 μg)/no AlPO4
- GBS6 (20 μg)/AlPO4
- GBS6 (20 μg)/no AlPO4
- Placebo

All safety and immunogenicity summaries in each stage of the study will be presented by a subset or complete set dependent on the study stage. In Stage 1 for primary vaccination, the subset will only include Groups 5 through 7; Stage 1 for booster vaccination will only include GBS6 (20  $\mu$ g)/AlPO4; Stage 2 will include all vaccine groups; Stage 3 will only include GBS6 (20  $\mu$ g)/no AlPO4 and placebo. Unless otherwise explicitly stated, all Stage 2 maternal participants from both sentinel and expanded cohorts will be combined, by vaccine groups listed above. Similarly, all Stage 2 infant participants from both sentinel and expanded cohorts will be combined according to their mother's vaccine group.

Both safety and immunogenicity results will be summarized separately for nonpregnant women with primary vaccination (Stage 1), nonpregnant women with a booster vaccination (Stage 1), maternal participants in Stage 2, maternal participants in Stage 3, infant participants in Stage 2, and infant participants in Stage 3. Immunogenicity data from Stage 3 will also be summarized separately by country (USA/UK, South Africa).

The GBS6 IgG antibody levels will be standardized as current quantitated values × correction factor. The lower limit of quantitation (LLOQ) values will be standardized as LLOQ = LLOQ × correction factor. The correction factors are set as follows: Ia, 0.46628125; Ib, 0.463392157; II, 1.451696809; III, 0.727236264; IV, 0.686258373; and V, 0.236850746. The standardized quantitated values will be reported for all analyses.

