#### Reporting results:

 Raw data: The number of participants with valid assay data (n), GMCs, and associated 2-sided 95% CI will be presented for each serotype.

Figures: The following figures will be based on the evaluable immunogenicity population only.

 Empirical RCDCs for the time points before and 1 month, 3 months, and 6 months after the booster vaccination will be generated separately for each serotype.

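### Stage 1 booster summaries pool first and second GBS6 doses: women given placebo at Visit 1 are reported as boosted

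*SAP*

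**What the plan says.** **Who receives the Visit 6 dose.** Stage 1 randomised about 22 women each to GBS6 with AlPO4, GBS6 without AlPO4, and placebo (Protocol 4.2, Table 2). Booster entry under Protocol 5.2 carries the condition "Participant must have received investigational product at Visit 1". Protocol 6 counts placebo as investigational product. Protocol 6.4 then states: "All returning participants in Stage 1 will also receive 1 dose of GBS6", at 20 µg per serotype with AlPO4. Exclusion criterion 11 (Protocol 5.3) bars any other GBS vaccine, so a protocol-compliant woman from the placebo arm has had no GBS vaccine before Visit 6.

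**Who is analysed.** None of the three booster populations looks at the Visit 1 product:
- Evaluable (SAP 4.1.1): "Have received a booster dose of GBS6", plus eligibility, blood-draw window, valid assay and no major violation.
- mITT (SAP 4.2.1): "The booster vaccination mITT population will include all randomized participants who received a booster dose", with at least one valid assay result.
- Safety (SAP 4.3.1): "All participants who received a booster dose of GBS6 will be included".

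**How results are grouped.** SAP 5.2 sets the rule for all safety and immunogenicity summaries: "Stage 1 for booster vaccination will only include GBS6" 20 µg with AlPO4. SAP 5.2.1.3 repeats it for the primary safety endpoints: "Stage 1 nonpregnant women with booster vaccination [1 vaccine group"]. Sections 6.1.1.1 to 6.1.1.4 and the antibody curves in 5.2.2.5 also specify one booster group. For booster IgG, SAP 6.2.1.2 says only "GMCs, and associated 2-sided 95% CI will be presented for each serotype", and the booster rows of Table 11 add no split.

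**A related line.** SAP 5.2.1.3 includes booster women among those for whom Tier 2 risk differences against placebo will be given. SAP 6.1.1.3 applies a Tier 2 risk difference to both the primary and the booster dose.

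**The concern.** Describing booster safety is a Stage 1 primary objective, and describing booster immunogenicity is a secondary one (Protocol 3.1.1 and 3.2.1). The reason given for adding the dose is that it is unknown whether GBS6 will be needed in every pregnancy (Protocol 2.2.5). A first dose does not inform that question. Stages 2 and 3 give a single dose, so the Visit 6 data are this study's only repeat-dose evidence.

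As written, both objectives are answered on a mix of first and second doses in a proportion the tables do not show. The safety denominator overstates how many women were observed after a second dose, and the GMCs and reverse cumulative curves cannot be read as the response to a second dose. The placebo risk difference has no comparator: the booster is open label with one product (Protocol 6.7), so the output would need an unstated control group.

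**Working it through.** **Inputs.** From the documents: 22 women per Stage 1 arm; booster numbers dependent on consent (Protocol 10.1), with returners per arm not given; exact Clopper-Pearson 95% intervals (SAP 5.2.1.3). Assumed: return rates, a reactogenicity difference, and the ratio of second-dose to first-dose GMC.

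**1. The plan's own figures.** Protocol Table 9 uses P(at least 1 event) = 1 − (1 − p)^n. For n = 44 at p = 1%, 2%, 5% this gives 0.357, 0.589, 0.895, against 0.36, 0.59, 0.90 in the table. For n = 22 it gives 0.198, 0.359, 0.677, against 0.20, 0.36, 0.68. The table reproduces.

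**2. Share on a first dose.** f = 22a / (22a + 44b), with a and b the return rates of the placebo arm and the two GBS6 arms.
- a = b: f = 1/3
- a = 0.5, b = 1: f = 11/55 = 0.20
- a = 1, b = 0.5: f = 22/44 = 0.50

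**3. Safety precision at full return.** The upper limit for 0/n is 1 − 0.025^(1/n).

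| Women | n | Upper limit, 0 events | P(≥1) at 1% | at 2% | at 5% |
|---|---|---|---|---|---|
| Pooled | 66 | 5.4% | 0.48 | 0.74 | 0.97 |
| Second dose only | 44 | 8.0% | 0.36 | 0.59 | 0.90 |
| One Visit 1 arm | 22 | 15.4% | 0.20 | 0.36 | 0.68 |

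**4. Reaction rates.** The pooled rate differs from the second-dose rate by f × (difference between first- and second-dose rates). For an assumed 10-point difference this is 3.3 points at f = 1/3, with a range of 2.0 (f = 0.20) to 5.0 (f = 0.50).

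**5. Post-booster IgG.** The GMC is a mean on the log scale, so pooled GMC / second-dose GMC = k^(−f), where k is the second-dose GMC divided by the first-dose GMC after Visit 6.

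| k (assumed) | f = 1/3 |
|---|---|
| 0.5 | 1.26 |
| 1 | 1.00 |
| 2 | 0.79 |
| 3 | 0.69 |

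At k = 3, the ratio runs from 0.80 (f = 0.20) to 0.58 (f = 0.50). Protocol 2.2.3.4, on a different GBS vaccine, describes a second dose that brought levels back to those after the first (roughly k = 1), with a 3-fold gain only in a subset with very low baseline. The documents give no k for GBS6.

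**6. Pre-booster IgG.** This is a named secondary time point. The pooled value averages women about 2 years after GBS6 with women who never had it. The same formula applies with a different ratio, also not given.

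**The case against.** The strongest reply is that the SAP follows the protocol. The protocol calls the Visit 6 dose a booster for every returner, and Protocol 10.3.1.1 defines the booster safety population as all who receive it. SAP 5.2 defines vaccine group by product, and only one product is given at Visit 6. That makes the labelling consistent, and it is why an all-recipients column should stay. It does not make a first dose informative about repeat dosing.

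Other points, and what stands of them:
- **Redaction.** A split by Visit 1 product could sit in SAP 6.3.2, in 6.5, in the redacted Stage 1 exploratory objectives and endpoints, or in table shells held separately. This stands, and limits the point to the readable primary and secondary summaries.
- **Silence.** SAP 6.2.1.2 and Table 11 state no booster grouping. True, but the rule in SAP 5.2 covers all immunogenicity summaries, and 5.2.2.5 states one group for the booster curves.
- **Assumed size.** Return rates, the 10-point gap and k are all assumptions; the shift in GMC may be nil or run in either direction. This stands. The overstated second-dose denominator needs only that some placebo-arm women return.
- **Descriptive analysis.** There are no hypotheses, booster data do not select the Stage 3 dose, and listings would allow a later split. True, but a descriptive table still has to describe the population named in its objective.
- **The risk difference is a separate drafting error.** Agreed; the pooling point does not rest on it.

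**Conclusion.** The concern holds for the readable primary and secondary booster summaries, and it must be fixed because a primary objective is affected. By design about one third of the booster group is on a first GBS6 dose; the share is 20% to 50% if arm return rates vary between 50% and 100%. With full return, second-dose exposure is 44 women, not 66, and the zero-event upper limit is 8.0%, not 5.4%. Post-booster GMCs could be unchanged (k = 1), lowered to 0.69 of the second-dose value (k = 3) or raised to 1.26 of it (k = 0.5), all at a one-third share. Without a split the reader cannot tell which applies. The Tier 2 comparison with placebo cannot be produced as written for the booster phase.

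**What to change.** In SAP 5.2, 5.2.1.3, 6.1.1, 6.2.1.2, 6.6 and Table 11:
- Present booster-phase safety and IgG results by Visit 1 product (GBS6 with AlPO4, GBS6 without AlPO4, placebo), and keep an all-recipients column for the protocol-defined booster safety population.
- Read the booster objectives from the columns of women who had GBS6 at Visit 1. Label the placebo column as a first GBS6 dose at Visit 6.
- Delete the booster-phase risk difference against placebo in 5.2.1.3 and 6.1.1.3.
- State that any comparison between women with and without earlier GBS6 is descriptive only, because returners are self-selected and the booster is open label.

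**Cost.** No new data. Visit 1 allocation is held, and under SAP 7.2 the study team is unblinded for Stage 1 from the first interim analysis. Adding columns means SAP text and table shells. A protocol amendment is also needed if the sponsor regards reading the primary objective from the GBS6-primed columns as a major change to a primary analysis (Protocol 10, SAP 2). The downside is precision: at most 22 women per arm and 44 with a second dose. At an observed 50%, the exact interval is 34.6% to 65.4% for 22/44 and 28.2% to 71.8% for 11/22, against 37.4% to 62.6% for 33/66.

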#### 3.6. Safety Endpoints

#### 3.6.1. Adverse Events

All AEs are collected on the case report form (CRF) for nonpregnant women (Stage 1), maternal participants (Stages 2 and 3), and infant participants (Stages 2 and 3) and will be categorized according to the current version (at the time of reporting) of MedDRA. For nonpregnant women (Stage 1), AEs will be collected following the primary and booster vaccinations separately.

An immediate AE is defined as any AE that occurred within the first 30 minutes after administration of the investigational product for nonpregnant women (Stage 1) and maternal participants (Stages 2 and 3) (see Section 8.8.2 [Immediate Adverse Events] of the protocol).

An MAE is defined as a nonserious AE that results in an evaluation at a medical facility. MAEs will be assessed from screening up to Visit 4 for nonpregnant women (Stage 1), from screening up to Visit 9 for maternal participants (Stages 2 and 3), and up to Visit 7 for infant participants (Stages 2 and 3). In addition, for participants receiving the booster vaccination in Stage 1, MAEs will be assessed from Visit 5 up to Visit 10.

AEs of special interest for infant participants (Stages 2 and 3) are major congenital anomalies, developmental delay, and suspected or confirmed GBS infection and are collected from birth through the end of the study (12-month postbirth visit). GBS infections that occurred during Days 1 through 7 are referred to as early-onset disease (EOD) and those that occurred during Days 8 through 90 are referred to as late-onset disease (LOD), where Day 1 is the day of birth.

AEs and SAEs will be captured and reported in accordance with Pfizer reporting standards and following the time period of collection outlined in Section 9.1.4 (Table 8) of the protocol.

A 3-tier approach will be used to summarize AEs. Under this approach, AEs are classified into 1 of 3 tiers. Different analyses may be performed for different tiers.

- Tier 1 events: These are prespecified events of clinical importance and, if any, are maintained in a list in the product's Safety Surveillance Review Plan. There are no preidentified Tier 1 events for this study.
- Tier 2 events: These are events that are not Tier 1 but are "common." A MedDRA
  preferred term is defined as a Tier 2 event if there are 4 or more participants in at least
  1 vaccine group.
- Tier 3 events: These are events that are neither Tier 1 nor Tier 2 events.

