#### 5. GENERAL METHODOLOGY AND CONVENTIONS

### 5.1. Hypotheses and Decision Rules

# 5.1.1. Statistical Hypotheses

This is a Phase 1/2 randomized, placebo-controlled, observer-blinded study to assess safety, tolerability, and immunogenicity of GBS6 in healthy nonpregnant as well as pregnant women and their infant participants. In all 3 stages of the study, no formal statistical hypothesis testing will be performed. An estimation approach will be used to assess the safety and immunogenicity objectives.

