### Reporting results:

 Raw data: The n and proportion will be presented for laboratory parameters (eg, hemoglobin, WBC) normal and for each grade (1 through 4), by vaccine group, for sentinel-cohort maternal participants from Stage 2 only.

Figures: None.

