# 6.1.2.4. Proportion of Maternal Participants Reporting AEs Through 1 Month After Administration of the Investigational Product

Endpoints: AEs experienced by maternal participants (Stages 2 and 3).

- Analysis time points: Day 1 to 1 month after vaccination.
- Analysis population: Safety population for maternal participants (Stages 2 and 3).
- Analysis methodology: Descriptive summary statistics.
- Supporting objective: Primary safety objective.

- Raw data: The number of participants with AEs (n), proportion, and associated 2-sided exact 95% CI will be presented for any AEs, SAEs, immediate AEs, severe AEs, related AEs, MAEs, and AEs leading to withdrawal, by vaccine group. Additionally, the number of participants with AEs (n), proportion, and associated 2-sided exact 95% CI will be presented for any AE, each SOC, and each preferred term within SOC, by vaccine group.
- Tier 2 AEs: The number of participants with AEs (n), proportion, risk difference, and associated 2-sided exact 95% CI will be presented for each preferred term.

Figures: None.

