#### Reporting results:

Raw data: The number of participants (n), proportion, and associated 2-sided exact 95%
 CI for each category will be displayed by vaccine group.

Figures: None.

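### Most placebo-controlled primary safety endpoints get one interval per arm and no vaccine-minus-placebo difference; the SAP's own risk-difference method could be extended to them cheaply

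*SAP*

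**What the plan says.** SAP 5.1.1 rules out hypothesis tests and states that "An estimation approach will be used to assess the safety and immunogenicity objectives". SAP 5.2.1.3 then makes two provisions for safety data. First, "the exact 2-sided 95% CIs using the Clopper and Pearson method will be provided by vaccine group for all primary safety endpoints". Second, a contrast with placebo by the Chan and Zhang method, limited in scope: "For Tier 2 AEs only, 95% CIs for the difference in proportions between each GBS6 vaccine group and placebo (risk difference".

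SAP 3.6.1 defines the tiers. A MedDRA "preferred term is defined as a Tier 2 event if there are 4 or more participants in at least" one vaccine group. It adds: "There are no preidentified Tier 1 events for this study".

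A Tier 2 reporting item appears in three primary-endpoint sections: 6.1.1.3 (Stage 1 AEs to 1 month), 6.1.2.4 (maternal AEs to 1 month) and 6.1.3.2 (infant AEs to 6 weeks). In each, the "proportion, risk difference, and associated 2-sided exact 95% CI will be presented for each preferred term".

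No such item appears in the other Stage 2 and 3 sections: 6.1.2.2 and 6.1.2.3 (reactions), 6.1.2.5 (SAEs, MAEs, obstetric complications), 6.1.2.6 (delivery outcome), 6.1.3.1 (birth outcomes) and 6.1.3.3 (infant SAEs, AESIs, MAEs to 12 months). For delivery outcome, for example, the "CI for each category will be displayed by vaccine group". The sentinel laboratory endpoint in 6.1.2.1 gets less: "The n and proportion will be presented for laboratory parameters", with no interval mentioned.

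**The concern.** Stages 2 and 3 randomise a concurrent placebo group. The quantity that randomisation protects is the difference between vaccine and placebo. As planned, a frequent preferred term can have that difference with an interval, while summary rows such as any SAE, premature live birth, stillbirth or a given infant AESI have none. Anyone looking for a signal in those rows has two separate intervals per comparison. Two overlapping 95% intervals do not show that the data are compatible with no difference, so an excess can pass unremarked. The plan also loses a plain statement of how large an excess the data cannot exclude.

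**Working it through.** **1. The plan's own figure.** The only sizing figure is Protocol Table 9, the chance of seeing at least one event: 1 − (1 − p)^n. For n = 14 and p = 10%, 1 − 0.9^14 = 0.771, matching the stated 77%. All 54 cells reproduce to rounding. The table concerns one group at a time and says nothing about between-arm precision.

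**2. Inputs.** Stage 3 has 108 per arm in Protocol 10.1. SAP Table 2 has 98 per arm, because the SAP rests on the preceding protocol amendment. Stage 2 has 40 per GBS6 group and 120 placebo. The documents give no event rates, so every count below is an assumption.

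**3. Who reaches Tier 2?** The chance that a group of n has at least 4 participants with a term of true rate p is P(X ≥ 4), X binomial(n, p). For n = 108 this is 0.024 at 1%, 0.171 at 2% and 0.794 at 5%. With both Stage 3 arms at 2%, the chance that at least one qualifies is 1 − (1 − 0.171)² = 0.31. A term at that rate therefore usually gets no difference.

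**4. Per-arm intervals against the difference.** The Clopper-Pearson limits are the 2.5% quantile of Beta(r, n − r + 1) and the 97.5% quantile of Beta(r + 1, n − r). The difference intervals invert two one-sided exact tests on the score statistic at 2.5% each (Chan-Zhang type). The exception is the first row, which uses the Miettinen-Nurminen score interval as a stand-in.

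| Vaccine vs placebo | Per-arm 95% CIs | Overlap | Difference, points (95% CI) |
|---|---|---|---|
| 12/108 vs 3/108 | 5.9-18.6%; 0.6-7.9% | yes | 8.3 (1.7 to 16.0) |
| 15/108 vs 5/108 | 8.0-21.9%; 1.5-10.5% | yes | 9.3 (1.5 to 17.8) |
| 22/108 vs 11/108 | 13.2-29.2%; 5.2-17.5% | yes | 10.2 (0.4 to 20.1) |
| 6/108 vs 0/108 | 2.1-11.7%; 0-3.4% | yes | 5.6 (1.5 to 11.9) |
| 7/40 vs 6/120 (Stage 2) | 7.3-32.8%; 1.9-10.6% | yes | 12.5 (1.3 to 28.0) |

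In every row the arms overlap and the interval for the difference excludes 0.

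**5. How often this happens.** Summing over all possible outcomes at 108 per arm, with true rates of 12% and 4%, the per-arm intervals separate in 22% of trials and the score interval for the difference excludes 0 in 61%. For 20% and 8% the figures are 34% and 74%. At 98 per arm they are 18% and 56%, then 31% and 69%, so the conclusion does not depend on which Stage 3 size applies.

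**6. Precision on offer.** With equal counts at 108 per arm, the exact interval for the difference is ±5.5 points at 3 vs 3, ±6.4 at 5 vs 5 and ±8.5 at 11 vs 11.

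**7. Laboratory endpoint.** For 0 of 14, the exact upper limit is 1 − 0.025^(1/14) = 23.2%. A table holding only n and proportion would show 0%.

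**8. Booster.** The Tier 2 sentence in SAP 5.2.1.3 includes the Stage 1 booster. SAP 5.2 gives the booster analysis a single GBS6 group, so no difference from placebo can be computed.

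**The case against.** The best defence is that the plan does what it sets out to do. The maternal objectives are to describe safety and the infant ones to assess it. Each primary endpoint is defined as a proportion, and per-arm proportions with exact intervals estimate precisely that. SAP 5.1.2 uses no decision rules, and SAP 6.7.1 treats safety analysis as exploratory. Nothing tells readers to judge by overlap, and the counts in both arms let anyone compute a difference. This stands as far as it goes: the plan does not contradict its objectives, and the figures in step 5 are a test-like yardstick that it disclaims. But a risk difference with an interval is an estimate, not a test, and it fits the stated estimation approach. The protocol's statement that no formal between-group comparison will be made is in 10.2.2, on immunogenicity. SAP 6.7.1 already accepts unadjusted AE differences.

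A reader might infer that no primary endpoint at all gets a contrast with placebo. The documents do not support that: the three AE endpoints named above do, by preferred term. Nor are serious or obstetric events shut out as such. Tier 2 depends on frequency, so such a term gets a difference once 4 participants in a group have it. SAP 5.2.1.3 and 6.7.1 set no 1-month or 6-week limit, so whether the 12-month tables would carry Tier 2 differences is unclear rather than excluded.

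On the laboratory table, 6.1.2.1 may simply fail to repeat the general promise in 5.2.1.3. That makes it a wording mismatch, and it lends no support to the between-arm point.

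**Conclusion.** The point holds as a gap in reporting, not as an error that invalidates an analysis. The summary rows of the Stage 2 and 3 primary endpoints outside the 1-month and 6-week AE sections have no planned vaccine-minus-placebo estimate. At the planned sizes, differences of roughly 6 to 12 points can sit behind overlapping per-arm intervals while the interval for the difference excludes 0. That size rests on assumed counts. It would be too strong to say that the trial's objective is safety relative to control, or that the plan breaks its own commitments on differences. Two narrower defects are internal to the text: the promised placebo difference for a booster analysis without placebo, and the missing interval for a primary laboratory endpoint. This is a cheap improvement worth making.

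**What to change.** Keep the Tier 2 sentence in SAP 5.2.1.3, but remove the booster from it and from the matching item in 6.1.1.3. Then add that the same Chan-Zhang 95% CI for the risk difference versus placebo will be given, descriptively and without multiplicity adjustment, at least for Stage 3, for these binary rows:

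- any SAE and any MAE (maternal and infant);
- obstetric complications by period;
- each delivery outcome, including premature live birth and stillbirth;
- binary birth outcomes: congenital anomaly, other neonatal problem, each vital-status category;
- each infant AESI;
- each local reaction and systemic event, as any and as moderate or worse.

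State that Tier 3 preferred terms, gestational age, Apgar and Ballard scores, and the Stage 1 booster are outside this addition. Simply deleting the Tier 2 restriction would not do: it would sweep in all of these. Separately, add exact CIs to 6.1.2.1 so that it matches 5.2.1.3 and Protocol 10.3.2.

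The cost is SAP wording and reuse of a method already planned, with no new data. The drawback is more unadjusted intervals to read, each of modest precision.
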